7.2.5 Sponsor Responsibility for Reporting Adverse Events

All Adverse Events will be reported to regulatory authorities, IRB/IECs and investigators in accordance with all applicable global laws and regulations. The Sponsor will inform Merck Global Safety in the appropriate timelines for reporting Adverse Events.

The PI will submit, once a year throughout the clinical trial, a safety report to the accredited METC.

This safety report consists of:

- a list of all suspected (unexpected or expected) serious adverse reactions, along with an aggregated summary table of all reported serious adverse reactions, ordered by organ system, per study.

a report concerning the safety of the patients, consisting of a complete safety analysis and an evaluation of the balance between the efficacy and the harmfulness of the medicine under investigation.

8.0 STATISTICAL ANALYSIS PLAN

8.1 Safety

Safety of the combination of SBRT and pembrolizumab will be assessed by the percentage of ≥ 3 pneumonitis. When combined SBRT and pembrolizumab treatment results in NCIC-CTC grade ≥ 3 pneumonitis in $\leq 10\%$ of patients, the combination is regarded as safe.

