1.0 TRIAL SUMMARY

Rationale: Despite the early stage of disease, a substantial number of patients with early stage non-small-cell lung cancer (NSCLC) relapse within five years of treatment. A pooled analysis of the ROSEL and STARS trials showed that stereotactic body radiotherapy (SBRT) may provide an alternative to surgical treatment for patients with early stage disease. One of the reasons for the favorable effects of SBRT may be due to an immunological response against tumor cells, elicited by radiotherapy. In this protocol we will explore the addition of immunotherapy to SBRT to augment the antitumor T cell response, associated with radiotherapy. Because surgical resection is still the current standard of care for patients who are fit to undergo surgery, the subjects will undergo a lobectomy with hilar and mediastinal lymph node dissection after SBRT +/- pembrolizumab treatment. This is a key feature of this study and an unique opportunity to perform histological examination of the entire lung tumor, its associated lymph nodes and normal lung tissue after immunotherapy, allowing the study of immune response heterogeneity and correlating this with non-invasive imaging and blood results. In the surrounding normal lung tissue, radiation and immunotherapy induced toxicity can be evaluated.

Objectives: To evaluate the safety and mechanisms of action of the trimodality treatment approach.

Study design: An open label randomized exploratory study of the safety and mechanisms of action of combined treatment with SBRT and immunotherapy (pembrolizumab, anti-PD1) for early stage NSCLC.

Estimated study duration: We expect to enroll one patient per month. Therefore, the study can be finished within 2.5 years from the time the first subject signs the Informed Consent Form (ICF) through the final contact.

Study population: Patients with histologically or cytologically confirmed diagnosis of early stage (T1N0 and T2aN0) peripherally located NSCLC, eligible for surgical resection.

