2.0 TRIAL DESIGN

2.1 Trial Design

This is an open label randomized exploratory study of the safety and mechanisms of action of combined treatment with stereotactic body radiotherapy (SBRT) and immunotherapy (pembrolizumab, anti-PD1) for early stage NSCLC. Because the mode of action of combined

SBRT and anti-PD-1 therapy is unknown, it is necessary to perform translational research to identify the mechanisms of action and toxicity before large, more expensive and time consuming effect size studies can be initiated with recurrence free and overall survival as outcome parameters.

[figure not shown]
Patients with early stage (T1bN0 and T2aN0) peripherally located and histologically confirmed NSCLC, eligible for surgical resection, will be enrolled in this study. Patients will be randomized between SBRT, with or without 2 cycles of pembrolizumab treatment (starting on the first day of radiotherapy). Because surgical resection is the current standard of care for these patients, the subjects will undergo a lobectomy with hilar and mediastinal lymph node dissection after SBRT +/- pembrolizumab treatment.

Surgical resection after the induction treatment is a unique opportunity to perform histological examination of the entire lung tumor and lymph nodes after immunotherapy, allowing to examine immune response heterogeneity and to correlate this with the non-invasive imaging and blood results. In the surrounding normal lung tissue, radiation and immunotherapy induced toxicity can be evaluated.

In week 8-10 after SBRT +/- pembrolizumab treatment, patients will undergo a lobectomy with hilar and mediastinal lymph node dissection. Patients randomized to 'no pembrolizumab treatment' will also undergo a resection 8-10 weeks after SBRT.

The primary endpoints of this study are safety of the trimodality approach and unraveling the immune mechanism of action. Serial invasive and noninvasive measurements of immunological biomarkers will be performed for the primary tumor, lymph nodes and peripheral blood. A study scheme is provided on page 11 of this protocol. The translational research will include biological imaging, immune effector subset examination and examination of healthy tissue for radiation induced changes.

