4.2.4 Rationale for Endpoints

This an exploratory study that aims to evaluate the safety of the trimodality approach and characterize the immunological mechanisms of action of combination radiotherapy and immunotherapy. Therefore the primary endpoints of this study are the tolerability and toxicity of combined SBRT +/- pembrolizumab treatment and surgery and to analyze the immunological antitumor response. The endpoints will be assessed by clinical signs of

radiation pneumonitis and examination of tumor core biopsies and resection material, FACS analysis on EBUS-FNA of TDLNs and peripheral blood to detect immunomodulation.

Secondary endpoints are the correlations of *in-vivo* PD-1 expression, quantified by immune-PET, with tissue and blood based immune-parameters.

The levels of PD-1 and PD-L1 expression are variable over time (see section 4.1.8) and expression has been found to be heterogeneous between and within tumor lesions of the same patient. The biomarker PD-L1 IHC is currently being validated in multiple clinical studies to stratify patients based on the intensity and percentage of positive staining. This trial is a unique opportunity to study the 3-dimensional uptake of ⁸⁹Zr-pembrolizumab in the tumor and correlate the imaging result with the 3D immunohistochemistry results of the surgical tumor specimen.

Although pneumonitis will be assessed as a symptom, an exploratory objective is to evaluate radiation induced changes to healthy lung tissue after SBRT +/- pembrolizumab treatment in the resected lung lobe.

The number of patients (n=10 in each arm) is too low to correlate study parameters to clinical outcome in terms of progression-free or overall survival.

4.2.5 ⁸⁹Zr-pembrolizumab imaging

To identify patients that will benefit the most from treatment with mAbs like pembrolizumab, better knowledge of the *in vivo* behavior of the drug is warranted. For this, positron emission tomography (PET) imaging with radiolabeled mAbs (immuno-PET) is an attractive option.

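### Safety of the three-part treatment, surgery included, is a stated primary aim, but grade ≥3 pneumonitis is the only clinical safety outcome Section 8 analyses, and its population and adverse-event window are not defined

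*Combined protocol and SAP*

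**What the plan says.** The primary safety aim is worded in two ways.

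- **Surgery included.** The objective in Section 1.0 is "To evaluate the safety and mechanisms of action of the trimodality treatment approach". Section 2.1 states: "The primary endpoints of this study are safety of the trimodality approach and unraveling the immune mechanism of action". Section 4.2.1 says the same in substance. Section 4.2.4 names surgery outright: "primary endpoints of this study are the tolerability and toxicity of combined SBRT +/- pembrolizumab treatment and surgery".
- **SBRT plus pembrolizumab only.** The main-endpoint paragraph of Section 1.0, Primary Objective 1 in 3.1, and 8.1 leave surgery out.

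On measurement, Section 4.2.4 says: "The endpoints will be assessed by clinical signs of" "radiation pneumonitis and examination of tumor core biopsies and resection material", together with flow cytometry. Section 8.1 then reads "Safety of the combination of SBRT and pembrolizumab will be assessed by the percentage of" grade ≥3 pneumonitis, and if this occurs in at most 10% "of patients, the combination is regarded as safe".

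Section 5.11 replaces subjects who do not undergo the trimodality treatment. Section 5.10 gives 30 days of adverse-event monitoring once treatment ends. Sections 7.2 and 7.2.3.1 give 90 days after treatment stops. Section 7.1.5.3.1 sets a visit about 30 days after the final dose and asks for all events before it, without saying that recording then stops. The flow chart in 6.1 marks adverse-event review at screening and induction, but not under surgery or follow-up.

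**The concern.** Section 4.1.7 says the authors know of no study that has combined SBRT, immunotherapy and resection. It expects no excess of fistula or other surgical complications. This trial's surgical safety data are therefore among its main products, yet no planned analysis would show whether that expectation was met.

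If 8.1 is followed as written, the only prespecified safety statement is that the combination is safe, and it depends on pneumonitis alone. Postoperative deaths, or resections abandoned because of a non-pneumonitis toxicity, would leave it unchanged. A reader could take it as the answer to the wider aim in 2.1 and 4.2.4.

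Two loose definitions add to this: who is in the denominator, and until when events are recorded.

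**Working it through.** **1. What Section 8 covers**

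| Outcome | Planned analysis |
|---|---|
| Grade ≥3 pneumonitis | 8.1, ≤10% rule |
| Fibrosis and infiltrate in resected lung | 8.2.1, by arm |
| CT lung density | 8.4, by arm |
| Immune-related events (yes/no) against organ SUV | 8.6, imaging correlation |
| Postoperative complications | none |
| Deaths | none |
| Resections cancelled or delayed | none |
| Any grade ≥3 adverse event | none |

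**2. What the 8.1 rule delivers.** Input: 10 patients per arm (5.2). The number of cases allowed is floor(0.10 × 10) = 1. Exact (Clopper-Pearson) 95% intervals are 0–30.8% for 0/10, where the upper limit is 1 − 0.025^(1/10), and 0.3–44.5% for 1/10. The chance of passing is (1−p)^10 + 10p(1−p)^9. At p = 10% it is 0.736, at 20% 0.376 and at 30% 0.149.

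**3. Events outside the rule.** Section 4.1.7 cites drug-related grade 3–4 events in 9.5% of pembrolizumab patients. Assuming that rate here, the chance of at least one in 10 patients is 1 − 0.905^10 = 0.63. Unless the event is pneumonitis, no safety analysis in Section 8 uses it.

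**4. Denominator (illustration only).** Suppose 11 patients receive the combination. One has grade ≥3 pneumonitis, misses surgery and is replaced; another has it and completes treatment. Counting everyone treated gives 2/11 = 18.2% (2.3–51.8%), and the rule fails. Counting completers only gives 1/10 = 10%, and the rule is met. Naming the treated population does not loosen the rule, because floor(0.10 × n) = 1 for every n from 10 to 19.

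**5. The 30-day window against surgery.** Inputs:
- Pembrolizumab every 3 weeks for 2 cycles from the first radiotherapy day (5.6.2), so the doses fall on days 1 and 22.
- SBRT every second day in 3 or 5 fractions (Table 2 in 5.6.1.2), so the last fraction falls on day 5 or 9.
- Flow chart (6.1): induction ends on day 56, described as 2 weeks after the second cycle. Hence cycle 2 ends on day 56 − 14 = 42. Surgery falls on days 56–70.

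| Treatment taken to end at | 30-day close | Against surgery on days 56–70 |
|---|---|---|
| Last dose, day 22 (combination) | 22 + 30 = 52 | 4–18 days before |
| Last fraction, day 5 or 9 (control) | 35 or 39 | 17–35 days before |
| End of cycle 2, day 42 (combination) | 42 + 30 = 72 | 2–16 days after |
| End of induction, day 56 | 56 + 30 = 86 | 16–30 days after |

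These days ignore the ±3-day dosing allowance and toxicity delays in 5.6.2.2. Surgery itself is dated differently across sections. Section 2.1 says of control patients that they "will also undergo a resection 8-10 weeks after SBRT", 5.6.3 counts from SBRT with or without pembrolizumab, and 6.1 gives study days.

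**The case against.** **Pneumonitis was chosen on purpose.** Section 4.2.4 names it, 8.1 matches Primary Objective 1, and the conclusion concerns the combination, not all three modalities. Pneumonitis arising after surgery would presumably count. This stands, and it is why the rule should stay. It does not remove the gap, because 4.2.4 itself puts surgery in the primary endpoint.

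**Toxicity is examined elsewhere.** A reader might infer that Section 8 looks at toxicity through pneumonitis and nothing else. That goes too far: 8.2.1, 8.4 and 8.6 are toxicity-related. They do not, however, cover surgical outcomes or overall grade ≥3 events.

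**Safety data are collected and reported.** Adverse events are graded throughout (7.1.2.1), and the yearly ethics-committee report in 7.2.5 includes an overall safety analysis and a table of serious adverse reactions. Section 5.13 allows early termination for adverse drug reactions. These are real safeguards, but 7.2.5 is regulatory reporting that specifies no population and no surgical outcome, and 5.13 does not alter the 8.1 conclusion.

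**Replaced patients.** A reader might infer that 5.11 removes a patient with pneumonitis from the denominator. No section says so. The natural reading of 8.1 is everyone given the combination, and 7.1.3 follows adverse events present at withdrawal. What stands is that the population is not named.

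**The 30-day text.** A reader might infer that monitoring always ends before surgery. Two of the four anchors above put its close after surgery, so the documents support only that the answer depends on an undefined term.

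**Surgical background.** Section 4.1.7 reports five planned resections after SBRT without complications (0/5: exact 95% CI 0–52.2%). It also cites at least four small salvage-surgery series, generally well tolerated, with one major toxicity. The evidence is thin, but it is more than five patients.

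**Conclusion.** The point holds as a gap in the planned analysis, and it should be fixed. Surgery-inclusive safety is a primary aim in four places, while Section 8 has one clinical safety outcome, and surgical results cannot change its conclusion. That conclusion is reached with 0 or 1 pneumonitis case in 10, where the upper 95% limit is 30.8% or 44.5%. The exploratory purpose excuses the missing power calculation, but not the lack of a descriptive summary for a primary endpoint.

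The population and the recording window are matters of clarification. Nothing in the text shows that the rule is biased or that surgical events go unrecorded. The figure of 10 combination patients comes from 5.2. The calendar figures assume on-schedule treatment and the flow chart's surgery days.

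**What to change.** 1. State one primary safety aim, in the same terms, in 1.0, 2.1, 3.1, 4.2.1, 4.2.4 and 8.1.
2. Keep the pneumonitis rule in 8.1, but word its conclusion as applying to pneumonitis, not to overall or trimodality safety.
3. Define the safety population for the rule and the table as all patients who started study treatment, by arm, including those replaced under 5.11.
4. Add a descriptive table by arm (n, %, exact 95% CI) of: any CTCAE v4.0 grade ≥3 adverse event; postoperative events by maximum grade; deaths from any cause; and resections cancelled, or done outside the protocol's surgical window, because of toxicity.
5. Reconcile 5.10, 7.1.5.3.1, 7.2, 7.2.3.1 and the flow chart into one recording window. It needs a defined anchor, the same in both arms, must extend past surgery, and needs a stated anchor for unresected patients. Sections 2.1, 5.6.3 and 6.1 must also be reconciled on what the 8–10 weeks are counted from, since item 4 depends on it.

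The cost is wording changes, one table, and slightly more data entry and tabulation. Intervals at 10 per arm will be wide. No between-arm test, new visit or clinical rule is proposed.

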5.2 Sample size

Twenty patients will be included in this study. A formal power analysis to calculate a sample size is not feasible due to the explorative nature of this trial. The sample size of 10 patients in each arm is based on two previous analyses that we performed. In a cohort of 9 head and neck cancer patients we were able to find significant differences in the expression of activation markers between different dendritic cell subsets (data on file). In a cohort of 9

melanoma patients we were able to find significant differences in the expression of activation markers between dendritic cell subsets of patients with a Breslow thickness more or less than 1.5 mm (60).

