7.1.1.7 Randomization

Patients will be randomized 1:1 by an automated program.

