10.3.5 Safety of the trimodality approach

Combining SBRT with surgery appears safe. At least 4 small studies have reported on patients who have undergone surgery for salvage in patients who have recurred after SBRT (42-45). Since the results of SBRT seem to be equivalent to those of surgery we believe that the delay to surgical resection is not harmful and might even be beneficial for patients. The addition of pembrolizumab to SBRT might lead to a higher rate of pneumonitis. However, the incidence of pneumonitis depends on the target volume and is rarely seen with treatment of early stage lung cancer. Because only patients with peripheral tumors are eligible for this trial and patients receive a lobectomy according to national guidelines on the treatment for NSCLC, the irradiated lung lobe will be resected and resection margins (i.e. central bronchial and vascular structures) are not involved in the radiation target volume.

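### Section 8.1 judges clinical pneumonitis in the combination arm alone, so the plan gives no estimate of what pembrolizumab adds to SBRT

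*Combined protocol and SAP*

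**What the plan says.** Section 8.1 is the whole of the planned safety analysis. It opens "Safety of the combination of SBRT and pembrolizumab will be assessed by the percentage of" grade 3 or higher pneumonitis and then gives the decision rule. The rule is worded for one arm ("When combined SBRT and pembrolizumab treatment results in NCIC-CTC grade" 3 or higher pneumonitis) and ends, at a rate of 10% or less, "of patients, the combination is regarded as safe". It names no comparator, difference, interval or test.

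Elsewhere the documents describe a controlled trial:

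- Section 7.1.1.7: "Patients will be randomized 1:1 by an automated program".
- Section 5.2: "Twenty patients will be included in this study", split 10 and 10, with no power calculation.
- Section 4.2.4: "the primary endpoints of this study are the tolerability and toxicity of combined SBRT +/- pembrolizumab treatment and surgery". The plus-or-minus sign covers both arms, and clinical signs of radiation pneumonitis are listed among the means of assessment.
- Section 10.3.5: "The addition of pembrolizumab to SBRT might lead to a higher rate of pneumonitis".
- Sections 8.2.1 to 8.2.3 and 8.4 each specify a comparison of SBRT with SBRT plus pembrolizumab, for immune markers, for fibrosis and infiltrate in resected lung, and for CT density.

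**The concern.** Sections 4.2.4 and 10.3.5 raise a question of added risk: does pembrolizumab increase pneumonitis over SBRT? A rate in one arm cannot answer it, because any pneumonitis due to SBRT itself counts in full towards the combination's total. The concurrent SBRT-only arm is the trial's only source for that background rate, since the documents give no figure and say only that pneumonitis is rare in early-stage treatment (4.1.7, 10.3.5).

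As written, the verdict does not depend on the control count. With 2 of 10 in both arms the combination is not regarded as safe, although nothing points to pembrolizumab. With 1 of 10 against 0 of 10 it is regarded as safe and no excess is estimated. Section 4.2.1 sees the results as a possible basis for work in stage III disease, where it calls radiation pneumonitis a feared complication. The added risk is what a later trial would want to know.

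**Working it through.** **Inputs from the documents.** There are 10 patients per arm (5.2), and the safe line is at most 10% (8.1). No alpha, power, effect size or SBRT-only rate is stated, so there is no power figure to reproduce. The planned 10 is used as the denominator.

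**Assumptions.** The shared true rate of grade 3 or higher pneumonitis is 2%, 5% or 10%. Tests are two-sided at 0.05.

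**Step 1: the rule in counts.** 10% of 10 is 1, so 0 or 1 event is regarded as safe and 2 or more is not.

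**Step 2: the rule when pembrolizumab adds nothing.** Both arms then share rate p, and

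P(2 or more of 10) = 1 - (1-p)^10 - 10p(1-p)^9.

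| Assumed p | (1-p)^10 | 10p(1-p)^9 | P(not regarded as safe) |
|---|---|---|---|
| 2% | 0.817 | 0.167 | 1.6% |
| 5% | 0.599 | 0.315 | 8.6% |
| 10% | 0.349 | 0.387 | 26% |

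The chance of an adverse verdict with no pembrolizumab effect therefore depends on the SBRT background rate, which 8.1 does not use.

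**Step 3: what a between-arm estimate would show.** The Newcombe interval combines the two Wilson intervals (l, u). With d = p1 - p2, where 1 is the combination and 2 is SBRT:

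- lower limit = d - sqrt[(p1 - l1)^2 + (u2 - p2)^2]
- upper limit = d + sqrt[(u1 - p1)^2 + (p2 - l2)^2]

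The Wilson 95% intervals are 0 to 0.278 for 0/10, 0.018 to 0.404 for 1/10, and 0.057 to 0.510 for 2/10.

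- 1/10 against 0/10: d = 0.10. Lower = 0.10 - sqrt(0.082^2 + 0.278^2) = -0.19. Upper = 0.10 + 0.304 = 0.40.
- 2/10 against 0/10: d = 0.20. Lower = 0.20 - sqrt(0.143^2 + 0.278^2) = -0.11. Upper = 0.20 + 0.310 = 0.51.

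**Step 4: would a test help?** Fisher's exact test on grade 3 or higher needs 5/10 against 0/10 (p = 0.033); 4/10 against 0/10 gives p = 0.087. Full enumeration gives power of 2.7% for 2% against 20%, and 2.0% for 5% against 20%.

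An exact Wilcoxon-Mann-Whitney test on worst grade was simulated for three assumed grade profiles (percent in grades 0/1/2/3/4):

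| SBRT only | Combination | Power |
|---|---|---|
| 50/33/15/2/0 | 20/30/30/15/5 | about 38% |
| 50/33/15/2/0 | 30/35/25/8/2 | about 15% |
| 85/8/5/2/0 | 60/10/10/15/5 | about 16% |

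The first two profiles give pneumonitis to half of the SBRT-only patients, which does not fit the protocol's description of it as rare. Neither test is a useful addition.

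**The case against.** The best defence is that 8.1 answers the objective as written. Objective 1 in section 3.1 concerns the safety of the combined treatment and carries no comparative hypothesis, whereas Hypothesis 2 does compare the arms. Section 5.2 bases the 10 per arm on immune-marker work: "The sample size of 10 patients in each arm is based on two previous analyses that we performed". An absolute rate is a legitimate target for a 20-patient exploratory study. This stands, and it is why the 10% rule need not be removed. It does not dispose of the added-risk question in 4.2.4 and 10.3.5, on which no analysis is planned.

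A reader might infer that the control arm is ignored for lung toxicity altogether. It is not. Section 8.2.1 compares fibrosis and infiltrate in the resected lobe, and 8.4 compares CT density and air fraction. Those comparisons cover tissue and imaging changes, which 4.2.4 itself separates from pneumonitis as a symptom.

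A reader might also infer that the rule will often condemn a harmless combination. At shared rates of 15% or 20% it would do so with probability 46% or 62%, but nothing in the documents suggests that SBRT alone causes severe pneumonitis that often in these patients.

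Finally, a between-arm contrast is only as good as its ascertainment. The trial is open label (9.3). The flow chart in 6.1 schedules on-treatment adverse event review by cycle, and only one arm has pembrolizumab cycles. The definitions in 7.2 and 7.2.3.1 are framed largely around pembrolizumab. This objection also stands: it weighs against any test driven by low-grade events, and the fix has to deal with it.

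**Conclusion.** The point holds for clinical pneumonitis only. Section 8.1 makes no use of the randomised SBRT-only arm, and no other section of the SAP compares the arms on clinical pneumonitis, so the plan yields no estimate of pembrolizumab's added risk. The 10% rule is not itself an error; it describes the combined regimen. Its dependence on the background rate is small at 2% (1.6%) and substantial at 10% (26%). Those rates are assumptions, because the documents give none. Ten per arm cannot settle the question: even 2/10 against 0/10 leaves an interval from -11 to +51 points. The gain is an honest estimate with its uncertainty, in place of a verdict that could be read as showing no added risk. The change should be made, but it does not call the design into question.

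**What to change.** Add to section 8.1:

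1. The number and percentage of patients with grade 3 or higher, and with grade 2 or higher, pneumonitis in each arm. Give the difference (combination minus SBRT) and its 95% Newcombe score interval, labelled descriptive.
2. A sentence that the 10% rule describes the combined regimen, and that any statement about added risk from pembrolizumab rests on the difference and not on the rule.
3. A statement, mirrored in 6.1 and 7.2, that pneumonitis is assessed and graded on the same schedule in both arms.

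Do not add a significance test. With power this low, a non-significant result could be misread as evidence of no added risk.

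The cost is SAP wording, one table and a clarification of the assessment schedule. Section 7.2.4 already has adverse events graded, and no extra patients are needed. The downside is that the intervals will be wide, so the safety conclusion will read less firmly.
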